Based on our prior research, comprehensive strategies are urgently needed to improve prediabetes care. Using these findings, we have designed and plan to implement a diabetes prevention clinical pathway which seeks to address some of these common clinician and patient barriers.

Study Objectives

Objective: Our primary objective to design and pilot test the diabetes prevention clinical pathway at a primary care clinic compared to a control primary care clinic.

Study Design

Overview: This is a non-randomized, quasi-experimental intervention study with one comparison group. Eligible patients include those on the prediabetes registry who are seen in the control and intervention clinics during the study period. Data is collected on eligible patients during the baseline (pre-implementation) period and prospectively during the 12-month implementation period.

Intervention Study Population Inclusion/Exclusion:

- Adults age 18 and older, on prediabetes registry, last A1c<6.5%
- Complete one visit (video or office visit) with PCP during intervention period

Blinding

While this study meets the NIH definition of a clinical trial, participants are not randomized or assigned at the patient level. The intervention is implemented clinic-wide and is intended to augment routine care (quality improvement). Therefore, the traditional terms of blinding in a clinical trial are not applicable.

Risks and Benefits

[figure not shown]
We believe the intervention involves minimal medical risk and is aligned with routine, evidence-based care. Participants may benefit from the intervention because of improved follow-up care (including visits, labs, and referrals) which may in turn result in a decreased risk of progression to diabetes. We aim to fill an important gap in knowledge about successful primary care clinic interventions to improve diabetes prevention. We hope to address the public health burden of diabetes by focusing on and improving the primary prevention of diabetes. We believe that the risks to subjects are low and reasonable given the anticipated benefits.

Withdrawal of Subjects

The intervention is intended to improve and augment routine care. Since it is implemented clinic-wide, patients will not have the option to opt out of the intervention. Furthermore, there is no outcome of treatment failure since we are not assigning patients to a particular treatment. They will receive treatments based on individual discussions with their doctor.

Study Procedures

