This is a pre-/post-evaluation of a diabetes prevention clinical pathway that will be implemented over a 12-month period at the intervention clinic. Eligible patients include those on the prediabetes registry who are seen in the control and intervention clinics during the study period. Their first visit with the PCP will be considered V0 (initial data collection) and data will be collected retrospectively (12 months prior to V0) and prospectively at that visit and subsequent primary care visits (V1, V2, V3, etc.) during the 12-month intervention period (see Figure).

The diabetes prevention clinical pathway will focus on the following steps: 1) Screen/test-testing of eligible patients for prediabetes/diabetes, 2) Education- PCPs will be encouraged to take an online learning module and in-person group training on prediabetes management, and patients with prediabetes will receive a handout about prediabetes prior to their upcoming PCP visit, 3) Action- PCPs will use a shared decision-making guide and treatment algorithm to discuss options with patients at their visit, 4) Referral- patients may be referred to DPPs and/or medical nutrition therapy (MNT), and 5) Treat- patients will be scheduled for a follow-up visit within 3-9 months with their PCP or care team (NP) to continue addressing prediabetes.

Group 1 Intervention clinic patients

PCPs in the intervention clinic will be invited and encouraged to attend the 1-hour clinician training session at the beginning of the intervention. This is considered continuing medical education, and we may be able to provide continuing medical education credit for their attendance. The training session will include information on prediabetes treatment guidelines, use of EPIC clinical decision support tools and use of the patient handout to discuss treatment options. There will be interactive skills practice incorporated. This training session may occur on up to 2 occasions to capture all PCPs. We may also record the training session so that PCPs who could not attend can view it later asynchronously.

Patients with prediabetes (e.g., “active” on prediabetes registry) presenting for a routine visit in the intervention clinic will be identified using an EPIC workbench report run the week prior to their upcoming visit. These patients, presenting for in-person or video visits, will receive the handout as an attachment either via MyChart or via email sent from REDCap.

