Enrolled participants will be monitored throughout the study for untoward incidents (e.g., “Adverse Events”) occurring during the study. The Principal Investigator (and other designated individuals, if necessary) will conduct regular monitoring for safety concerns and provide general oversight for human subject safety requirements. Where necessary these occurrences will be evaluated for severity, attribution, and possible trends. All adverse events that are anticipated or described in the informed consent form will be logged appropriately and reported to the IRB on at least an annual basis (e.g., at continuing review).

Any Unanticipated Problems or unexpected “Serious Adverse Events” *related* to the study intervention or affecting the risk/benefit profile of the study, will be reported to the IRB promptly, and, in all cases, within 10 business days of discovery. Unplanned and non-emergent deviations from the IRB approved protocol will be logged and reported to the IRB annually at continuing review; all planned deviations will be submitted as a Change in Research to the IRB for approval and prior to implementation. All other event reporting requirements will be followed and all necessary parties will be notified of events/problems encountered in the study and/or changes in research, in accordance with all applicable regulations and guidelines.

Statistical Plan

Sample Size Determination and Power

We estimate that 1200 patients with prediabetes will be seen over the 12-month intervention period within each clinic (total sample of 2400 patients). Based on this sample, we estimate we will have 100% power to detect a change in rate of referral to DPPs from 0% to 25%. Additionally, we estimate that we will have 100% power to detect a change in documented prediabetes diagnosis from 10% (baseline rate estimated from Johns Hopkins data) to 34% (national estimate of the prevalence of prediabetes), follow-up lab testing completed from 50% (baseline rate estimated from Johns Hopkins data) to 60%, and referral to nutrition from 1% (baseline rate estimated from Johns Hopkins data) to 10%. In our analysis, we will assess the differences in trend of the outcomes in the baseline, intensive implementation, and sustainment periods.

Primary outcome variable

The primary outcome is whether patients with prediabetes are referred to a DPP and/or medical nutrition therapy and/or start metformin.

Secondary outcome variables

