The secondary outcomes are whether patients: 1) enroll in the DPP, 2) attend a medical nutrition therapy visit, 3) complete follow-up glycemic testing, 4) fill metformin, 5) achieve weight loss $\geq 5\%$ and 6) complete PCP/team follow-up visit.

Other process outcomes we will look at include whether MyChart messages with the prediabetes handout are read.

Statistical Methods

For the analysis, we will include patients with prediabetes (identified by prediabetes registry) who have completed at least once PCP visit during the first 6 months of the 12-month intervention period. We will compare the primary outcomes and other secondary outcomes between the intervention and control clinics.

We will conduct an interrupted time series analysis to evaluate the differences in trend of the outcomes in the baseline (V0-12m), intensive implementation (T0-T6m), and sustainment periods (T6m-T12m) at the patient level. We will compare these outcomes in the pre- and post-intervention periods using logistic regression models with generalized estimating equations to account for repeated observations within patients. We will use multivariate logistic regression models to determine predictors of these outcomes adjusting for race, age, and baseline HbA1c. We may adjust for clinic-level characteristics, such as patient safety culture using GLINT survey data from 2021 and 2022 if available. We will only request aggregate data from the clinic-level on safety culture.

Study Administration

Funding Source

Funding for this study is provided by the National Institute of Diabetes and Digestive Kidney Diseases under Award Number K23DK118205 (PI: [name]).

Subject Stipends and Payments

Patients who complete the survey will receive a \$10 gift card, either mailed to their home address or sent as an e-gift card based on patient preference. The last survey question will ask them to provide this information, which will not be linked to other responses. Clinicians who

complete the survey will get a \$25 e-gift card sent to the email address they provide. Again, their response to this question will not be linked to other responses.

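### Sample size and power are stated for patients seen over 12 months, but the analysis set is those seen in the first 6 months; that set also makes the intensive and sustainment periods unequal in opportunity for the primary outcome

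*Combined protocol and SAP*

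**What the plan says.** Three sections describe who counts.

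- Inclusion/Exclusion (Study Design) sets no time limit within the intervention period: "Complete one visit (video or office visit) with PCP during intervention period".
- The sample-size section of the Statistical Plan states: "We estimate that 1200 patients with prediabetes will be seen over the 12-month intervention period within each clinic (total sample of 2400 patients". It claims 100% power on that sample for four changes: DPP referral 0% to 25%, documented diagnosis 10% to 34%, follow-up lab testing 50% to 60%, and nutrition referral 1% to 10%.
- Statistical Methods restricts the analysis to registry patients "who have completed at least once PCP visit during the first 6 months of the 12-month intervention period". It gives neither an expected number nor a reason.

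Statistical Methods then plans an interrupted time series over the "baseline (V0-12m), intensive implementation (T0-T6m), and sustainment periods (T6m-T12m) at the patient level". The outcome concerned is defined under Primary outcome variable: "The primary outcome is whether patients with prediabetes are referred to a DPP and/or medical nutrition therapy and/or start metformin".

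The statistical text does not define T0. Study Design, Overview fits a clinic start date: "Data is collected on eligible patients during the baseline (pre-implementation) period and prospectively during the 12-month implementation period". Study Procedures anchors each patient on the first visit, "Their first visit with the PCP will be considered V0 (initial data collection"), and collects data "prospectively at that visit and subsequent primary care visits (V1, V2, V3, etc.) during the 12-month intervention period".

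Planned prediabetes follow-up visits are described for the pathway only: within 3-9 months in the Study Procedures overview, and 3-6 months under Group 1. Those two intervals need reconciling; both are used below. The Group 2 (control) text describes usual care and no such visit.

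**The concern.** There are two separate problems.

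First, a reader will take 1200 per clinic as the analysed number and 100% as the power of the planned analysis. Both belong to a wider set, and the size of the set actually analysed is unknown.

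Second, the entry rule is tied to one of the two periods being compared. Referral and metformin start are actions taken largely at visits. Every analysed patient has at least one visit in T0-T6m by selection. None needs one in T6m-T12m, and patients first seen after month 6 are left out. The proportion with an action can therefore differ between periods although clinicians do the same thing at each visit. Generalized estimating equations deal with correlation within patients, not with this selection. The Introduction says that success would lead to implementation across the health system, so a sustainment result produced, or masked, by the entry rule matters.

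**Working it through.** **1. Stated power.** Inputs: 1200 per clinic and the four pairs of rates, from the sample-size section. The documents give no significance level; two-sided 5% is assumed, with independent observations. For n per clinic and p̄ the mean of p1 and p2,

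power = Φ{ [ |p1 − p2|·√n − 1.96·√(2p̄(1 − p̄)) ] / √(p1(1 − p1) + p2(1 − p2)) }.

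Lab testing, 50% to 60%: 1.96·√(2·0.55·0.45) = 1.379, and √(0.25 + 0.24) = 0.700.

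- n = 1200: (3.464 − 1.379)/0.700 = 2.98, power 99.86%.
- n = 600: (2.449 − 1.379)/0.700 = 1.53, power 93.7%.

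| n per clinic | Lab testing | Other three |
|---|---|---|
| 1200 | 99.9% | 100.0% |
| 900 | 99.0% | 100.0% |
| 800 | 98.1% | 100.0% |
| 720 | 96.9% | 100.0% |
| 600 | 93.7% | 100.0% |

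The stated 100% is reproduced at 1200. Lab testing rounds to 100% (at least 99.5%) only from 1013 per clinic, which is 1013/1200 = 84% of the 12-month count. It stays at 90% or more down to 519 (43%).

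The size of the first-6-months set has to be assumed. If each patient is seen once at a uniformly distributed time, it is half, or 600. If visits occur at random at λ per year, the share is (1 − e^(−λ/2))/(1 − e^(−λ)), which is 0.62 at λ = 1 and 0.82 at λ = 3, or about 745 to 980.

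**2. Period comparison.** All inputs are assumed: T0 is clinic start, the chance q of referral or metformin start is constant at 6% per visit, and a patient counts in a period if at least one such action occurs in it (repeats allowed). With k visits the probability is 1 − (1 − q)^k: 6.0% for one visit, 11.64% for two.

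*Random visits, 1.5 per year (0.75 per half-year).* T6m-T12m: 1 − e^(−0.75·0.06) = 4.4%. T0-T6m, given at least one visit: 4.4%/(1 − e^(−0.75)) = 4.4%/0.528 = 8.3%.

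*Planned follow-up at 3-6 months.* Entry is uniform over months 0-6, each follow-up comes 3-6 months after the last visit, and there are no other visits. With full attendance 25% of patients have a second visit before month 6, so T0-T6m is 0.75·6.0% + 0.25·11.64% = 7.4%. With 50% attendance (the sequence ends at a missed visit) 12.5% do, giving 0.875·6.0% + 0.125·11.64% = 6.7%. The T6m-T12m figures in these rows are simulated.

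| Visit pattern (assumed) | T0-T6m | T6m-T12m |
|---|---|---|
| Random, 1 per year | 7.5% | 3.0% |
| Random, 1.5 per year | 8.3% | 4.4% |
| Random, 3 per year | 11.1% | 8.6% |
| 3-6 month follow-up, full attendance | 7.4% | 7.5% |
| 3-6 month follow-up, 50% attendance | 6.7% | 3.0% |
| 3-9 month follow-up, full attendance | 6.7% | 5.5% |
| 3-6 month follow-up, 80% attendance, plus 1.5 random visits per year | 9.2% | 9.7% |

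If T0 is instead the patient's first visit, that visit always falls in T0-T6m. Random visits at 1.5 per year then give 1 − 0.94·e^(−0.045) = 10.1% and then 4.4%, or less where month 12 cuts the second period short.

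**3. The control clinic.** Take 25% per visit in the intervention clinic and 6% in control, both assumed.

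- Same random visits (1.5 per year) in both clinics, repeats counted: 32.4% then 17.1% against 8.3% then 4.4%. The risk ratio is 3.9 in both periods; the odds ratio, the scale of the planned model, is 5.3 then 4.5.
- Same visits, first events only, referred patients kept in the denominator: the second period becomes (1 − 0.324)·17.1% = 11.6% against (1 − 0.083)·4.4% = 4.0%. The risk ratio is 3.9 then 2.9.
- Full 3-6 month attendance in the intervention clinic (29.7% then 30.1%), random visits in control: 29.7/8.3 = 3.6, then 30.1/4.4 = 6.8.

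In each case nothing changed per visit.

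**The case against.** The strongest reply is that the rule has an evident purpose. Entry by month 6 leaves at least 6 months of follow-up, which suits weight loss, repeat testing and the follow-up visit. That is plausible, though unstated, and it is a reason to keep the cohort for those outcomes. It does not carry over to a primary outcome that can occur at the first visit.

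The planned follow-up visits also bring intervention patients back in T6m-T12m, and with good attendance the fall disappears. This stands. A reader might infer that the rule must produce an apparent loss of effect in the sustainment period; the documents do not support that, because they give neither visit rates nor attendance.

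The main question is clinic against clinic, and both clinics share the entry rule. That limits the damage. But a reader might infer that the control clinic cancels the artefact, and this is not supported either, since the planned visits are described for one clinic only. Those extra visits are part of the pathway, so they belong in its overall effect; they still blur any statement about delivery per visit.

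Finally, the Study Procedures figure is not available here and may define T0. Its absence is not held against the plan, and the selection argument holds on either reading.

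**Conclusion.** The concern holds in two limited parts.

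*Size and power.* The 1200 and the 100% are not those of the planned analysis set. This is an unreconciled definition and a missing number. A reader might infer an underpowered study; the figures do not show that. Only lab testing, a secondary outcome, moves, and it keeps 93.7% even if the set is half the stated size. This rests on a two-sided 5% level and an assumed 600.

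*Periods.* The entry rule gives unequal opportunity for the primary outcome in T0-T6m and T6m-T12m, so a within-clinic difference, or its absence, cannot be read as evidence about sustainment. The magnitude is open: across the assumed patterns the second period runs from less than half the first to slightly above it. The calculation assumes a constant chance per visit and one fixed cohort followed through both periods, which is the natural reading of a patient-level comparison. The plan should be changed, but the clinic comparison itself is not invalidated.

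**What to change.** 1. State the expected number per clinic in the first-6-months set, restate power for it with the significance level, and label the 1200 as the 12-month eligible count. Give the reason for the rule, and define T0 in the statistical text.

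2. For the primary outcome, apply the same visit-based entry rule to T0-T6m and T6m-T12m, including the already eligible patients first seen after month 6. In each period count only patients not yet referred or started on metformin at its start, or analyse per visit up to the first event (the form to use if T0 is the first visit). With random visits at 1.5 per year this gives 8.3% in both periods at 6% per visit and 32.4% in both at 25%. Keep the first-6-months cohort for outcomes that need follow-up, and as a sensitivity analysis for the primary outcome.

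3. Report the intervention-versus-control contrast within each period, with visit counts per period by clinic. Do not draw a sustainment conclusion from the within-clinic change alone.

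Cost: SAP wording, one patient count and slightly more analysis; the additional records are already to be collected. Late entrants have less follow-up. With uniform entry over months 6-12, 25% would reach a 3-6 month visit by month 12 (12.5% for 3-9 months), against 100% (87.5%) of first-6-months entrants. A small fall remains if patients differ in how readily they are referred: 31.1% then 28.6% in one assumed case (mean 25% per visit). That is a further reason for item 3.

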**Implementation and Evaluation of a Diabetes Prevention
Clinical Pathway in Primary Care**

NCT05265312

Date: 7/11/2023

Introduction

Abstract and Background:

Prediabetes is a significant public health problem affecting 88 million U.S. adults. Evidence suggests that the vast majority of people with prediabetes are unaware that they have this condition and many are not receiving appropriate care for prediabetes, including referral to evidence-based programs like the Diabetes Prevention Programs. In our retrospective cohort study of patients with prediabetes from Johns Hopkins Health Systems, we found that the rates of prediabetes clinical care activities are low. In our qualitative studies, we found that primary care physician (PCP) barriers include low knowledge about Diabetes Prevention Programs and misperceptions of insurance coverage of these programs and inadequate clinical staff to address prediabetes. Common patient barriers to taking action to prevent diabetes include lack of motivation, time and resources.

Primary Hypothesis: We hypothesize that the clinical pathway will result in increased clinician screening and intervention and improve patient engagement in diabetes prevention. We will compare results from the intervention clinic compared to a control clinic. If successful, we plan to implement and test the effectiveness of this clinical pathway across the entire health system.

Purpose of the Study Protocol: As described above, we have conducted several studies to understand current practices in prediabetes care across the Johns Hopkins Health Systems. In our retrospective cohort study of patients with prediabetes from Johns Hopkins, we found that the rates of prediabetes clinical care activities are low. Within 12 months, 63.4% had repeat glycemic testing, yet only 10.4% had coded diagnoses of prediabetes, 1.0% were referred for nutrition services, and 5.4% were prescribed metformin. We were unable to evaluate uptake of Diabetes Prevention Programs (DPPs) since a referral order was not in place until recently. In our qualitative studies, we found that clinician barriers include low knowledge about DPPs and misperceptions of insurance coverage of these programs and inadequate clinical staff to address prediabetes. Common patient barriers to taking action to prevent diabetes include lack of motivation, time and resources.

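### The interrupted time series has no time bins, slopes or clinic-by-time terms, and its baseline overlaps implementation, so unequal secular growth in referrals could be credited to the pathway

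*Combined protocol and SAP*

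**What the plan says.** Statistical Methods describes an "interrupted time series analysis to evaluate the differences in trend of the outcomes in the baseline (V0-12m), intensive implementation (T0-T6m"), followed by a sustainment period from T6m to T12m, at patient level. Sample Size Determination and Power repeats the aim: "we will assess the differences in trend of the outcomes in the baseline, intensive implementation, and sustainment periods".

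The model then named is a logistic GEE contrasting before with after, which allows for repeat records on a patient. A further logistic model adjusts for race, age and baseline HbA1c. The between-clinic comparison stands in a separate sentence and is not tied to the time series. No month or quarter, slope term, clinic-by-time term or check of pre-implementation trends is given.

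Study Procedures defines the baseline from each patient's first PCP visit: "data will be collected retrospectively (12 months prior to V0"). The analysis set requires a PCP visit in the first six months of the intervention year, so V0 lies between T0 and T6m.

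The design is non-randomized, with one clinic per group (Study Design, Overview). On DPP uptake, the Introduction says that "a referral order was not in place until recently". Control-clinic PCPs can also refer to DPPs and have the same Epic tools (Group 2).

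**The concern.** An interrupted time series separates an intervention effect from a trend already under way. It needs several time points before the interruption, and a controlled version needs them in both groups. The plan names one baseline period and gives it no internal time unit.

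This matters more than usual here. With one clinic per group and no randomization, the pre-implementation course of the two clinics is the main evidence that the control clinic shows what would have happened without the pathway. DPP referral is part of the primary outcome and its order is recent, so referrals may still be rising in both clinics, and nothing in the plan shows that they rise equally. If the intervention clinic was already rising faster, a comparison of period averages would count that as effect.

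The mixed anchors add a second problem. The baseline moves with each patient's V0 while the later periods are fixed in calendar time, so the same calendar month can be baseline for one patient and implementation for another.

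**Working it through.** **1. The plan's own figure.** The expected numbers, under Sample Size Determination and Power, are these: "We estimate that 1200 patients with prediabetes will be seen over the 12-month intervention period within each clinic (total sample of 2400 patients"). A two-proportion power calculation with 1200 per clinic and two-sided alpha 0.05 (assumed; the plan states none) gives:

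| Outcome | Change | Power |
|---|---|---|
| DPP referral | 0% to 25% | 100.0% |
| Documented diagnosis | 10% to 34% | 100.0% |
| Follow-up lab testing | 50% to 60% | 99.9% |
| Nutrition referral | 1% to 10% | 100.0% |

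The stated 100% reproduces. It is power to compare two proportions, not to compare trends.

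**2. Can the named periods carry a trend?** A two-clinic segmented model with a break at T0 needs level, slope, level change and slope change in each clinic: 4 × 2 = 8 parameters. Three periods in two clinics give 6 cells, and the design matrix has rank 6, so the pre-slopes are not identified. Monthly bins (12 before, 12 after) give 48 cells and rank 8. With a second break at T6m the model has 12 parameters, and monthly bins give rank 12.

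**3. Overlap of baseline and implementation.** The share of a patient's look-back that falls after T0 is V0/12. The maximum is 6/12 = 50%. With V0 uniform over T0-T6m (assumed), the mean is 3/12 = 25%.

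On the same assumption, the V0-anchored extract covers 8%, 25%, 42%, 58%, 75% and 92% of the cohort in the six months from T0-12m to T0-6m, then 100% in each of the six months before T0.

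**4. False effect from unequal growth, using the three periods.**

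- Mean V0 is +3 months, so the baseline is centred at 3 − 6 = −3. The later periods are centred at +3 and +9. The gaps are 6 and 12 months.
- False effect = gap × slope difference g. The documents give no g; 0.1 to 0.5 points per month is assumed.
- Base rate: 6% (assumed). The Introduction's 1.0% nutrition referral plus 5.4% metformin makes 6.4% if the two do not overlap and DPP referral is zero.
- SE of the difference in change = √(4 × 0.06 × 0.94 / n), treating cells as independent: 1.94 points for n = 600 and 1.37 for n = 1200. The 1200 is the plan's twelve-month count; 600 is half of it, because the analysis set requires a visit in the first six months.
- False-positive rate = Φ(d/SE − 1.96) + Φ(−d/SE − 1.96), where d is the false effect.

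| g (points/month) | Period | False effect (points) | n = 600 | n = 1200 |
|---|---|---|---|---|
| 0.1 | T0-T6m | 0.6 | 6% | 7% |
| 0.1 | T6m-T12m | 1.2 | 9.5% | 14% |
| 0.3 | T0-T6m | 1.8 | 15% | 26% |
| 0.3 | T6m-T12m | 3.6 | 46% | 75% |
| 0.5 | T0-T6m | 3.0 | 34% | 59% |
| 0.5 | T6m-T12m | 6.0 | 87% | 99% |

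**5. What the calendar-month model can deliver.** Assume 100 patients per clinic-month (1200/12) and 7% monthly events, so the variance of a monthly between-clinic difference is 2 × 0.07 × 0.93/100 = 0.001302.

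- Pre-slope difference: the sum of squared deviations of 12 monthly points is 143, so SE = √(0.001302/143) = 0.30 points per month. Power for a difference of 0.3 is about 17%; 80% power needs 2.8 × 0.302 = 0.84.
- Level change at T0, one break: variance factor 2 × (1/12 + 36/143) = 0.670, SE = √(0.670 × 0.001302) = 3.0 points, detectable at 80% power 2.8 × 2.95 = 8.3 points.
- Level change at T0, breaks at T0 and T6m: factor (1/12 + 36/143) + (1/6 + 9/17.5) = 1.016, SE = 3.6 points, detectable 2.8 × 3.64 = 10.2 points.

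**The case against.** The strongest reply is that the plan is under-specified rather than incapable. It speaks of trend in the baseline, works at patient level, and allows for several records per patient; nowhere does it say the baseline is reduced to one value. It collects twelve months of record data in both clinics, and step 2 shows that monthly bins identify every parameter. This stands. A reader might infer that no pre-implementation slope or parallel-trends check is possible. The documents do not support that. Even the V0-anchored extract covers the whole cohort in the last six months before T0. Its thin early months cost precision and shift the cohort's make-up, but they do not make a slope inestimable.

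Second, growth common to both clinics cancels once a clinic-by-period term is fitted. This also stands: only unequal growth biases that contrast, and its size is unknown. That the order is recent makes growth plausible; it does not show that the clinics differ.

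Third, the result depends on where the baseline is centred. A centre of −6 months would give larger false effects, but it requires every V0 to fall at T0, contrary to a spread over six months.

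Fourth, drift of this size is small beside the planned DPP change ("100% power to detect a change in rate of referral to DPPs from 0% to 25"%). True: it threatens modest effects, not one of 25 points.

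Fifth, overlap with the period after T0 might be taken to mean that baseline data are contaminated by the pathway. V0 is the patient's first PCP visit, so the look-back largely precedes that patient's own exposure. The established problem is that calendar time is mixed.

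**Conclusion.** The concern holds as a gap in specification together with a misaligned baseline. Used as three categories, the periods named cannot yield the promised trend comparison, and a two-clinic contrast built on them has no protection against unequal secular growth.

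For slope differences of 0.1 to 0.5 points per month, the false effect is 0.6-3.0 points in T0-T6m and 1.2-6.0 points in T6m-T12m. False-positive rates are 6-34% and 9.5-87% with 600 per clinic, and 7-59% and 14-99% with 1200, against a nominal 5%. These figures rest on four assumptions: the slope difference, V0 uniform over T0-T6m, a 6% base rate and independent cells. They show what the design as written would let through, not that such growth occurred.

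**What to change.** Anchor all periods to T0. Extract, in both clinics, all registry patients with a PCP visit from T0-12m to T0+12m, including those seen only before T0. Bin by calendar month and date each outcome by its order.

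Fit a segmented logistic GEE clustered on patient, with clinic-by-time, clinic-by-level-change and clinic-by-slope-change terms at T0 and, to keep the sustainment period, again at T6m. State which of these terms is the pathway effect.

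Report the pre-T0 clinic-by-time term as an estimate with its confidence interval, not as a pass/fail test; at about 17% power for a 0.3-point difference, a non-significant result would reassure falsely. If DPP referral was near zero for part of the pre-period because the order did not yet exist, say so, since the pre-slope for that component then tells little.

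The cost is revised SAP wording, a wider EHR query and lower precision. The SE of the T0 level change is about 3.0 points with one break and 3.6 with two. That remains adequate for the planned 25-point change, if that change applies to a month's patients, but not for effects of only a few points.
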